# 7.4.2.7. Regulatory Reporting Requirements for SAEs

Prompt notification of SAEs by the investigator to GSK is essential so that legal obligations and ethical responsibilities towards the safety of patients are met.

GSK has a legal responsibility to notify both the local regulatory authority and other regulatory agencies about the safety of a product under clinical investigation. GSK will comply with country-specific regulatory requirements relating to safety reporting to regulatory authorities, Independent Ethics Committees (IEC) and investigators.

Investigator safety reports will be prepared for suspected unexpected serious adverse reactions according to local regulatory requirements and GSK policy and will be forwarded to investigators as necessary.

An investigator who receives an investigator safety report describing an SAE(s) or other specific safety information (e.g., summary or listing of SAEs) from GSK will file it with the IB and will notify the IRB/IEC, if appropriate according to local requirements.

### 7.4.3. Pregnancy Testing, Prevention, and Reporting

#### 7.4.3.1. Pregnancy Testing and Prevention

The need for a screening pregnancy test depends on whether a female patient is of childbearing potential or non-childbearing potential.

A female of non-childbearing potential (i.e., physiologically incapable of becoming pregnant) is defined as any female who has had a hysterectomy, bilateral oophorectomy (ovariectomy) or bilateral tubal ligation, or is post-menopausal.

A practical definition accepts menopause after 1 year without menses with an appropriate clinical profile, e.g., age appropriate, >45 years in the absence of hormone-replacement therapy (HRT). In questionable cases, the patient must have a follicle-stimulating hormone (FSH) value >40 mIU/mL and an estradiol value <40 pg/mL (<140 pmol/L).

A female of child-bearing potential is defined as any female who does not meet the criteria of non-childbearing potential as described in the previous paragraph.

If a female patient is of childbearing potential, she must have a serum  $\beta$ -human chorionic gonadotropin (HCG) pregnancy test performed within 14 days prior to randomisation. Patients with a positive pregnancy test result must be excluded from the study. Patients with a negative pregnancy test result must agree to use an effective contraception method

as described below throughout the treatment period and until 4 months after the last dose of study treatment.

- GSK acceptable contraceptive methods, when used consistently and in accordance with both the product label and the instructions of the physician, are as follows:
- An intrauterine device with a documented failure rate of less than 1% per year.
- Vasectomised partner who is sterile prior to the female patient's entry and is the sole sexual partner for that female.
- Complete abstinence from sexual intercourse for 14 days prior to randomisation, throughout the treatment period, and for at least 4 months after the last dose of study treatment.

**Note:** Abstinence is acceptable only when in line with the preferred and usual lifestyle of the patient. Periodic abstinence (e.g., calendar, ovulation, symptothermal, post-ovulation methods) and withdrawal are not acceptable methods of contraception.

• Double-barrier contraception: condom and occlusive cap (diaphragm or cervical/vault caps) with a vaginal spermicidal agent (foam/gel/cream/suppository).

**Note:** Hormonal-based methods (e.g., oral contraceptives) are not permitted due to potential drug-drug interactions with dabrafenib.

Female patients who are nursing must discontinue prior to randomisation and must refrain from nursing throughout the treatment period and for 4 months after the last dose of study treatment.

# 7.4.3.2. Pregnancy Reporting

Any pregnancy that occurs during study participation must be reported using a clinical trial pregnancy form. To ensure patient safety, each pregnancy must be reported to GSK within 2 weeks of learning of its occurrence. The pregnancy must be followed-up to determine outcome (including premature termination) and status of mother and child. Pregnancy complications and elective terminations for medical reasons must be reported as an AE or SAE. Spontaneous abortions must be reported as an SAE.

Any SAE occurring in association with a pregnancy brought to the investigator's attention after the patient has completed the study and considered by the investigator as **possibly related** to study treatment, must be promptly reported to GSK.

In addition, the investigator must attempt to collect pregnancy information on any female partners of male study patients who become pregnant while the patient is enrolled in the study. Pregnancy information must be reported to GSK as described above.

# 7.4.4. Laboratory Assessments

All protocol-required laboratory assessments must be conducted in accordance with the Time and Events Schedule (Table 19). Only local laboratory assessments are undertaken during the course of the trial and its data must be recorded in the patients CRF.

Clinical chemistry and haematology parameters to be tested are listed in Table 22. Female patients of child-bearing potential will have a serum pregnancy test at Screening; urine pregnancy testing may be done during study treatment, if necessary.

# Table 22 Clinical Chemistry and Haematology Parameters

#### **Clinical Chemistry Parameters**

- Albumin
- Alkaline Phosphatase
- Alanine Transaminase (ALT) or Serum Glutamic Pyruvic Transaminase (SGPT)
- Aspartate Aminotransferase (AST) or Serum Glutamic Oxaloacetic Transaminase (SGOT)
- Gamma-Glutamyl Transpeptidase (GGT)
- Blood Urea Nitrogen (BUN) or urea
- Calcium
- Creatininec
- Lactate Dehydrogenase (LDH)
- Phosphate
- Potassium
- Sodium
- Total Bilirubinb
- Total Protein

#### **Haematology Parameters**

- White Blood Cell (WBC) Count
- Hemoglobin
- International Normalized Ratio (INR; at Screening only)a
- Platelet Count
- Prothrombin Time (PT; at Screening only)a
- Partial Thromboplastin Time (PTT; at Screening only)a
- Automated WBC Differential (expressed as %):
  - o Basophils
  - Eosinophils
  - Lymphocytes
  - Monocytes
  - Neutrophils
- Coagulation panel to be done at Screening only.
- b. Bilirubin fractionation is recommended if total bilirubin is > 2 x the upper limit of normal (ULN).
- c. If serum creatinine is > 1.5 mg/dL, creatinine clearance should be calculated using the standard Cockcroft-Gault formula (Appendix 2).

For patients with a history of chronic HBV and/or HCV, the following tests will be performed at Screening:

- Viral hepatitis serology;
- Hepatitis B surface antigen and Hepatitis B core antibody (IgM); and/or
- Hepatitis C RNA.

# 7.4.5. Ophthalmic Examination

Patients are required to have a standard ophthalmic examination performed by an ophthalmologist at baseline and as clinically warranted per protocol's guidance (Section 5.8.5.4). The exam will include indirect and/or direct fundoscopic examination, visual acuity (with correction), visual field examination, and tonometry, with special attention to retinal abnormalities that are predisposing factors for RVO or CSR.

In patients with clinical suspicion of RVO or CSR, fluorescent angiography and/or optical coherence tomography are highly recommended.

# 7.4.6. Vital Signs

Vital sign measurements will include systolic and diastolic blood pressure, body temperature, pulse rate, body weight, and height (only at Screening). Body temperature, weight and height measurements should be recorded in the metric scale.

All blood pressure assessments should be performed under optimal conditions i.e. after (i) patient has been seated with back support, ensuring that legs are uncrossed and flat on the floor, (ii) patient is relaxed comfortably for at least 5 minutes, (ii) preparatory steps including removal of any restrictive clothing over the cuff area and selection of the right cuff size have been ensured, (iii) the arm is supported so that the middle of the cuff is at the heart level, and (iv) the patient remains quiet during the measurement. In patients with an initial blood pressure reading within the hypertensive range, a second reading should be taken at least 1 minute later, with the 2 readings averaged to obtain a final blood pressure measurement. Only the averaged value should be entered in the eCRF.

# 7.4.7. Physical Examinations

Complete physical examination will include assessments of eyes, neurological and cardiovascular systems, lungs, abdomen, and any other areas with signs and symptoms of disease, and of the head, neck, ears, nose, mouth, throat, thyroid, lymph nodes, extremities, and a full skin exam to assess cutaneous malignancies and proliferative skin diseases. Complete physical examinations will also include thorough genitourinary (pelvic) and rectal exams to assess secondary malignancies. In females, the pelvic exam must visualize the cervix. Pap smear and colposcopy are performed at the investigator's discretion. Rectal exam must include digital rectal exam and visual inspection of the anus and perianal area. Brief physical examinations will include assessment of head, neck, eyes, skin, neurological and cardiovascular systems, lungs, abdomen, and any other areas with signs and symptoms of disease. Refer to the Time and Events Table (Table 19) for when to perform a complete or a brief physical examination.

Dermatologic skin exams may be referred to a dermatologist, if needed.

If possible, the same physician should perform each examination for the duration of the study to ensure consistency between evaluations (i.e., if the patient is referred to a Dermatologist for the Screening examination, the Dermatologist should do all follow-up dermatologic skin assessments).

# 7.4.8. Electrocardiograms (ECG)

Twelve (12)-lead ECGs will be obtained using an ECG machine that automatically calculates heart rate and measures PR, QRS, QT, RR and QTcB intervals.

At each assessment, a single 12-lead ECG will be performed by qualified site personnel after the patient has rested in a semi-recumbent or supine position for at least 5 minutes.

See Section 5.8.3.3 for instructions if QTc withholding criteria are met.

# 7.4.9. Echocardiograms (ECHO)

Echocardiograms (ECHO) will be performed to assess cardiac ejection fraction and cardiac valve morphology. If possible, ECHO should be performed by the same person throughout the study for a patient. The echocardiographer's evaluation should include an evaluation for left ventricular ejection fraction and both right and left-sided valvular lesions.

#### 7.5. Pharmacokinetics

As part of the secondary objectives of this study, concentrations of trametinib and of dabrafenib and its metabolites (GSK2285403, GSK2298683, and GSK2167542) will be determined at each time point during treatment when the skin and tumour biopsies are performed. During the monotherapy treatment in arm A and B, only trametinib or dabarafenib and its metabolites will be measured. During combination, both drugs and metabolites will be measured.

#### 7.5.1. Blood Sample Collection for Pharmacokinetics

Blood samples for PK analyses of dabrafenib, trametinib, and metabolites of dabrafenib will be collected at the same day as the tumour and skin biopsies are performed during treatment (Week 2, 8 and 10). Patients with morning clinic visits will be instructed to withhold their morning dose, and samples will be collected prior to dabrafenib and trametinib administration; for patients with afternoon clinic visits, patients will take their morning doses as usual, and samples will be collected 4-8 hours following dabrafenib and trametinib administration. Date and exact time of pharmacokinetic sample and of most recent dose will be recorded. No more than 25 mL of blood will be collected over the duration of the study for PK blood sample collection, including any extra assessments that may be required.

Details of PK blood sample collection (including volume to be collected), processing, storage, and shipping procedures will be provided in the SPM.

2012N132406\_01 **CONFIDENTIAL**BRF116613

# 8. DATA MANAGEMENT

For this study, patient data will be entered into GSK defined Inform eCRFs, transmitted electronically to GSK or designee and combined with data provided from other sources in a validated data system.

Management of clinical data will be performed in accordance with applicable GSK standards and data cleaning procedures to ensure the integrity of the data, e.g., removing errors and inconsistencies in the data. Adverse events, concomitant medications terms and other anti-cancer therapies will be coded using Medical Dictionary for Regulatory Activities (MedDRA) and an internal validated medication dictionary, GSKDrug.

eCRFs (including queries and audit trails) will be retained by GSK and copies will be sent to the investigator to maintain as the investigator copy. In all cases, patient initials will not be collected or transmitted to GSK in accordance with GSK policy.

## 9. DATA ANALYSIS AND STATISTICAL CONSIDERATIONS

# 9.1. Hypotheses

The primary objective of this trial is to evaluate the percentage reduction of pERK score from baseline and characterise safety and efficacy of different treatment sequence with the pERK score changes. The primary end point will be analysed with a descriptive intent only. Hence no hypothesis testing will be performed.

# 9.2. Study Design Considerations

#### 9.2.1. Sample Size Assumptions

Based on feasibility a sample size of 54 patients will be enrolled in this trial in 1:1:1 ratio to one of the three treatment arms allowing a total of 20% early dropout rate. Assuming as large as 30% standard deviation (s.d.) of percentage reduction of pERK score from baseline, 15 patients per treatment arm will be sufficient to ensure that the 95% confidence interval (CI) will be the mean  $\pm 16.61\%$ . With 15 patients per treatment arm, the study will have >97% power to detect 80% reduction of pERK score from baseline to Week 2 within a treatment group (with s.d.=70%, alpha=0.05, two sided paired t-test).

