#### 7.2. Biomarkers

Comparative examination of pre-dosing profiles of patients may uncover known or novel candidate biomarkers/profiles which could be used to predict response to study treatments or provide new insights into melanoma and medically related conditions. Comparative examination of post-dosing profiles in conjunction with pre-dosing profiles may yield known and novel candidate biomarkers/profiles and new insights which relate to the action of the study treatments and changes contributing to the development of resistance.

Novel candidate biomarkers and subsequently discovered biomarkers of the biological response associated with melanoma or medically related conditions and/or the action of the study treatments may be identified by application of DNA/gene, RNA and protein analysis of tumour tissue.

Unless stated otherwise, these investigations may be performed irrespective of whether a response to study treatment is observed.

Biopsies will be performed on cutaneous or sub-cutaneous lesions that are easily accessible and will NOT be performed on any deep lesions. If possible biopsies should be taken from the same lesion/location. Key biopsies are taken at randomisation, week 2, week 8, and week 10. Additional patients might be recruited to ensure a sufficient number of patients in each arm providing these three key biopsies.

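### 54 patients with the stated 20% dropout leave 14.4 per arm, not the 15 on which the stated precision and power rest; the effect is small

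*Protocol*

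**What the plan says.** Protocol 9.2.1 fixes the total on practical grounds: "Based on feasibility a sample size of 54 patients will be enrolled in this trial", allocated 1:1:1 "to one of the three treatment arms allowing a total of 20% early dropout rate". That is 18 patients per arm.

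The same paragraph then describes what 15 patients per arm would give:

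- **Precision.** "Assuming as large as 30% standard deviation (s.d.) of percentage reduction of pERK score from baseline", it says "15 patients per treatment arm will be sufficient to ensure that the 95% confidence interval (CI) will be the mean" ± 16.61%.
- **Power.** With 15 per arm, "the study will have >97% power to detect 80% reduction of pERK score from baseline to Week 2 within a treatment group", taking an SD of 70% and a two-sided paired t-test at 0.05.

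Protocol 9.2.2 (Table 23) extends the precision figure to SDs from 10% to 50%. SAP 5.1 and 5.2 (Table 1) repeat all of this. Protocol 9.1 and SAP 2.3 say that the primary endpoint is analysed descriptively, with no hypothesis test.

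**The concern.** The dropout rate and the number per arm stand in adjacent sentences, and a reader will take the second to be what is left after the first. It is not: 18 patients less 20% is fewer than 15. The total of 54 is what results from adding 20% to 45 (three arms of 15), whereas allowing for a 20% loss means dividing 45 by 0.8. The documents do not show which step was used, so this explanation is an inference from the numbers.

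In a trial without hypothesis tests, the number of patients expected per arm and the half-width it gives are the main planning statements. If they are quoted for a number that the stated dropout does not leave, the plan claims slightly better precision than it should expect.

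**Working it through.** **Inputs (Protocol 9.2.1):** N = 54, three equal arms, 20% dropout, 15 per arm for precision and power. SD is 30% for precision. For power, the effect is 80% and the SD 70%, two-sided alpha 0.05, paired t-test.

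**1. Reproduce the plan's own figures at n = 15.**

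- Half-width = t(0.975, n − 1) × SD / √n = 2.145 × 30 / √15 = 16.61. This matches the stated value.
- For SDs of 10, 20, 30, 40 and 50 the same formula gives 5.538, 11.076, 16.613, 22.151 and 27.689. All five rows of Table 23 match.
- Power from the noncentral t distribution with n − 1 degrees of freedom and noncentrality (80/70) × √n is 98.4%, consistent with the stated figure of more than 97%.

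**2. Apply the stated dropout to the stated total.**

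- 54 × 0.8 = 43.2 patients; 43.2 / 3 = 14.4 per arm. In whole patients, 43 split as evenly as possible is 14, 14 and 15.

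**3. Work back from 15 per arm.**

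- 15 / (1 − 0.20) = 18.75, so 19 per arm and 3 × 19 = 57 in total.
- 45 × 1.2 = 54, the plan's number.
- Loss that 54 can absorb while keeping 45: 1 − 45/54 = 16.7%, or 3 of 18 per arm.

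**4. Effect on precision and power.**

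| n per arm | Half-width at SD 30% | Power (80% effect, SD 70%) |
|---|---|---|
| 15 (as stated) | 16.61 | 98.4% |
| 14.4 (expected at 20% loss) | 17.03 | 98.0% |
| 14 | 17.32 | 97.6% |

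The half-width grows by 0.4 points (17.03 − 16.61) to 0.7 points (17.32 − 16.61).

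**5. Precision table at n = 14.** For SDs of 10, 20, 30, 40 and 50: 5.77, 11.55, 17.32, 23.10 and 28.87.

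**The case against.** The strongest reply is that 54 was never presented as derived from a precision target. It rests on feasibility, Protocol 3 and 4.1.1 call it approximate, and the sentence about 15 per arm only describes what 15 would deliver. The gap is 0.6 patient per arm, no test or between-arm comparison depends on it, and the range of SDs in Table 23 moves the half-width far more (5.5 to 27.7). This stands as an argument that the effect is small. It does not make the figures agree: feasibility explains 54, but not how a 20% loss from 54 leaves 15 per arm.

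A second reply is that Protocol 7.2 provides a remedy: "Additional patients might be recruited to ensure a sufficient number of patients in each arm providing these three key biopsies". The clause is permissive and gives neither a number of extra patients nor a target per arm, so it does not restore 15.

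Three stronger readings are tempting, and the documents do not support them:

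- **That ±16.61% or Table 23 is miscalculated.** Both are exact for n = 15, the number for which 9.2.1 states the precision.
- **That unusable or missing biopsies make the shortfall much larger.** Some such loss is plausible, since footnote 22 of the Time and Events Table leaves biopsies to the investigator's judgement. The documents give no rate for it, so any figure would rest on an assumption from outside the plan.
- **That the word three in 7.2, after a list of four time points, lets the top-up be met without a Week 8 sample.** Appendix 7 shows that the amendment added Week 8 to a list of three and left the count unchanged. It is an editorial leftover, and it has no bearing on a half-width defined in 9.2.2 for baseline to Week 2.

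**Conclusion.** The point holds as a mismatch between two stated planning figures. With 54 randomised and 20% lost, the plan should expect 14.4 patients per arm; 15 per arm is compatible with a loss of at most 16.7%.

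The size is minor: a half-width of about ±17.0% to ±17.3% at SD 30% instead of ±16.61%, with the power statement still true at 14 per arm. It does not show that the design fails or that enrolment must rise to 57.

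The result takes the 20% as a proportion of randomised patients spread evenly over the arms, counts every remaining patient as evaluable at baseline and Week 2, and keeps the plan's SDs.

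**What to change.** Keep N = 54 and make the same change in Protocol 9.2.1 and SAP 5.1, choosing one of two statements:

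1. 54 patients allow for a loss of up to 16.7% (3 of 18 per arm) while keeping 15 per arm. The half-width, the power statement and the precision tables then stay as they are.
2. With 20% early dropout, about 14 patients per arm remain, giving a half-width of about ±17.3% at SD 30%; the power statement is then made for 14 per arm and remains above 97%. Replace the five values in Protocol Table 23 and SAP Table 1 with 5.77, 11.55, 17.32, 23.10 and 28.87.

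In either case, add the n per arm to the table caption, which does not state it at present. The cost is a sentence in each document and, under the second option, five recomputed numbers and a slightly less favourable precision. No procedure, visit or enrolment target changes.

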# 9.2.2. Sample Size Sensitivity

The effect of changes in the assumed standard deviation on the precision (i.e., half-width of the 95% CI for percent reduction of pERK score from Baseline at Week 2 within a treatment group) is summarised in Table 23.

Table 23	Effects of changes in the assumption of standard deviation
I UDIO EU	Elicoto di changoo ili tilo accamptioni di ctanadia actiation

Standard Deviation (%)	Precision (Half-width of 95% CI of % reduction of pERK score from baseline within a treatment group)				
10	5.538				
20	11.076				
30	16.613				
40	22.151				
50	27.689				

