#### 9.3.5. Key Elements of Analysis Plan

The final analysis will be performed after the last patient has the week 16 efficacy assessment

Data will be listed and summarised according to the GSK reporting standards, where applicable. Complete details will be documented in the RAP. Any deviations from, or additions to, the original analysis plan described in this protocol will be documented in the RAP and final study report.

Demographic and baseline characteristics will be summarised.

Percentage reduction in pERK biomarker score from baseline to Week 2 will be calculated within a treatment group.

ORR will be determined based on confirmed responses. Details on the determination of tumour response are given in Section 7.3.4.

PFS analysis will be performed if there is sufficient number of events at the time of final analysis. For the analysis of PFS, if the patient received subsequent anti-cancer therapy prior to the date of documented progression or death, progression free-survival will be censored at the last adequate assessment (e.g. assessment where visit level response is CR, PR, or SD) prior to the initiation of therapy. Otherwise, if the patient does not have a documented date of progression or death progression-free survival will be censored at the date of the last adequate assessment. Further details on rules for censoring will be provided in the RAP.

Duration of response analysis will be performed if there is sufficient number of responders.

Additional details on biomarker analyses are provided in Section 9.3.5.1. Similarly additional details on efficacy and safety analyses are provided in Section 9.3.5.2. and in Section 9.3.5.3 respectively.

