#### 9.3.5.1. Biomarker Analyses

Biomarker endpoints are defined in Section 2. Percentage reduction of pERK score from baseline is the primary endpoint of this study. Change in biomarker status is most prominent within two weeks of start of treatment. Patients from arm A and arm B will be given combination therapy starting from week 9 after completion of 8 weeks of monotherapy. Therefore, changes in biomarker between screening and week 2 as well as between week 8 and week 10 will be summarised. In addition, effect of change of biomarker status on ORR will be determined. Further details will be provided in the RAP.

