5. SAMPLE SIZE CONSIDERATIONS

5.1. Sample Size Assumptions

Based on feasibility a sample size of 54 patients will be enrolled in this trial in 1:1:1 ratio to one of the three treatment arms allowing a total of 20% early dropout rate. Assuming as large as 30% standard deviation (s.d.) of percentage reduction of p-ERK score from baseline, 15 subjects per treatment arm will be sufficient to ensure that the 95% confidence interval (CI) will be the mean \pm 16.61%. With 15 patients per treatment arm, the study will have > 97% power to detect 80% reduction of p-ERK score from baseline to Week 2 within a treatment group (with standard deviation (STD) =70%, alpha=0.05, two sided paired t-test).

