5.2. Sample Size Sensitivity

The effect of changes in the assumed standard deviation on the precision (i.e., half-width of the 95% CI for percent reduction of p-ERK score from Baseline at Week 2 within a treatment group) is summarized in [Table 1](#).

Table 1 Effects of changes in the assumption of standard deviation

Standard Deviation (%)	Precision (Half-Width of 95% CI of % reduction of pERK score from baseline within a treatment group)
10	5.538
20	11.076
30	16.613
40	22.151
50	27.689

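### SAP 11.2.1 and its tables summarise the baseline-to-Week-2 p-ERK change for Arm C only, although Protocol 9.3.5 and SAP 11.2 plan it without an arm limit; the size statement also uses two unexplained SDs

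*Protocol*

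**What the plan says.** **Endpoint and planned analysis.** Protocol Section 2 (Table 1) and SAP 2.2.1 make the percentage change in p-ERK score from baseline the primary endpoint. Protocol 9.3.5 says: "Percentage reduction in pERK biomarker score from baseline to Week 2 will be calculated within a treatment group". Protocol 9.3.5.1 says that "changes in biomarker between screening and week 2 as well as between week 8 and week 10 will be summarised". SAP 11.2 repeats this and adds that the changes will be listed. None of the three names an arm.

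SAP 11.2.1 is narrower. It assigns the summary of actual and percent change from baseline to two weeks to Arm C, and the Week 8 to Week 10 change to Arms A and B.

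**Size.** Protocol 9.2.1 argues: "Assuming as large as 30% standard deviation (s.d.) of percentage reduction of pERK score from baseline, 15 patients per treatment arm will be sufficient" to give a 95% CI of the mean ±16.61%. The next sentence claims more than 97% "power to detect 80% reduction of pERK score from baseline to Week 2 within a treatment group", with the inputs "with s.d.=70%, alpha=0.05, two sided paired t-test". Protocol 9.2.2 describes the tabulated precision as the "half-width of the 95% CI for percent reduction of pERK score from Baseline at Week 2 within a treatment group".

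SAP 5.1 carries both SDs over, including "70%, alpha=0.05, two sided paired t-test" for the power. SAP 5.2 Table 1, "Effects of changes in the assumption of standard deviation", repeats Protocol Table 23. Both tables run from an SD of 10% to 50%.

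**The concern.** For Arms A and B, Week 2 is the only early on-treatment biopsy that shows the effect of each drug alone against an untreated baseline. Protocol 9.3.5.1 itself says that the biomarker moves most in the first two weeks of treatment. The Week 8 to Week 10 contrast answers a different question: what adding the second drug does to a patient who has already had eight weeks of the first. If tables are programmed from SAP 11.2.1 and the display list, the report will not summarise the primary endpoint's change from baseline in two of the three arms.

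On the size statement, a reader cannot tell which spread the sponsor expects. Precision is shown only under the smaller SDs and power only under the largest one. If 70% is the realistic value, the quoted precision is too optimistic by a factor of 70/30.

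**Working it through.** **Step 1. Which p-ERK summaries cover Arms A and B?**

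| Source | Baseline to Week 2 change | Week 8 to 10 change |
|---|---|---|
| Protocol 9.3.5 | within a treatment group, no arm limit | not mentioned |
| Protocol 9.3.5.1 and SAP 11.2 | no arm limit | no arm limit |
| SAP 11.2.1, summary statistics | Arm C | Arms A and B |
| SAP 11.2.1, mixed model | combination arm (screening and Week 2) | monotherapy-first arms |
| SAP Table 5.0031 and V600E Table 5.0071 | upfront-combination arm | not covered |
| SAP Table 5.0030 and V600E Table 5.0070 | not covered | monotherapy-first arms |

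What remains at Week 2 for Arms A and B:
- Table 5.0021, which summarises score levels at Week 2
- the mean and median time plots (Figures 15.0010 and 15.0020)
- a percent-change-from-baseline column in Listing 25.0010 (mock-up HScore10)

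Levels and plots of means do not give the within-patient percent change, and the listing does not summarise it. Table 5.0120 groups best response by category of percent change in H-score, but its title names no interval and it reports response, not the change.

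Planned patients affected: 54/3 = 18 per arm, so Arms A and B are 2 × 18 = 36 of 54.

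**Step 2. Is the interval used to argue the size reported anywhere?** The mock-up for the change tables (HScore3) gives mean, SD, median, minimum and maximum, with no confidence interval. The mixed model gives 90% limits for ratios of geometric means. No listed p-ERK display gives a 95% CI for the mean percent change.

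**Step 3. Reproduce the plan's precision figures.** The half-width is t(0.975, n−1) × SD/√n. With n = 15, t(0.975, 14) = 2.1448 and √15 = 3.8730, this is 0.55378 × SD.

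| SD (%) | Half-width (%) | In Table 23 and SAP Table 1 |
|---|---|---|
| 10 | 5.538 | yes, matches |
| 20 | 11.076 | yes, matches |
| 30 | 16.613 | yes, matches |
| 40 | 22.151 | yes, matches |
| 50 | 27.689 | yes, matches |
| 60 | 33.227 | not shown |
| 70 | 38.765 | not shown |

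Ratio of the half-widths at the plan's own two SDs: 38.765/16.613 = 2.33.

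**Step 4. Reproduce the power.** For a paired t-test with effect 80, SD 70, n = 15 and two-sided alpha 0.05, the noncentral t distribution gives 98.4%, and simulation also gives 98.4%. This agrees with the stated >97%.

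**Step 5. Are the two SDs for the same quantity?** Protocol 9.2.2 defines the precision as that of the percent reduction from baseline at Week 2 within a treatment group. The power sentence concerns the reduction from baseline to Week 2 within a treatment group. The texts point to one quantity, but neither says so. The precision sentence in 9.2.1 names no time point, and the 70% appears only as a parameter of the t-test.

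**The case against.** **The SAP does plan the Week 2 change.** A reader might infer from Tables 5.0030 and 5.0031 that the SAP plans no summary of the Week 2 change in Arms A and B. The documents do not support that. SAP 11.2 says this change will be summarised and listed without an arm limit, and SAP 7 says biomarker endpoints are evaluated for each arm. This objection stands. The defect is a conflict between SAP 11.2 and SAP 11.2.1 with its display list. It still needs settling, because the display list is what specifies the output.

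**Nothing is miscalculated.** A reader might also infer that the sample size is wrong or the trial underpowered. It is not. All five tabulated rows and the power reproduce from their stated inputs. The size rests on feasibility, and Protocol 9.1 plans no hypothesis test. Computing power at the larger SD is also cautious: at an SD of 30% the power is essentially 100%. This stands, and it confines the SD point to the planning statement.

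**The 70% may belong to another scale.** The power sentence does not name its variable, so this cannot be excluded. No other scale is stated, however, and the 30% is presented as an upper value for the percent reduction, so a single quantity is the more natural reading.

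**The 95% CI can be derived.** Mean, SD and count are enough to calculate it, so printing it is partly a preference. But that is possible only for arms whose change is summarised, which at present means Arm C.

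**The 36 patients are planned, not evaluable.** The analysis uses the Biomarker Population, and biopsies are taken at the investigator's judgement (Protocol Table 19, footnote 22). The number with paired Week 2 samples is unknown and may be lower.

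**Conclusion.** The main point holds as an inconsistency. SAP 11.2.1, Tables 5.0030 and 5.0031 and V600E Table 5.0071 are narrower than Protocol 9.3.5, Protocol 9.3.5.1 and SAP 11.2. Followed as written, they leave the primary endpoint without a paired baseline-to-Week-2 change summary in two of three arms, nominally 36 of 54 patients. It should be resolved before the database freeze.

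The SD point holds as a secondary matter of clarity. Two values, 30% and 70%, are used without explanation. If both describe the Week 2 percent reduction, the precision at 70% is ±38.8% and not ±16.61%, which is 2.33 times wider. That assumes n = 15 per arm, a t-based interval and a single quantity; the last is indicated by Protocol 9.2.2 but not stated. Neither point changes enrolment, the sample size or the >97% power.

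**What to change.** 1. Amend SAP 11.2.1 to agree with SAP 11.2 and Protocol 9.3.5 and 9.3.5.1. Summarise the actual and percent change from baseline to Week 2 in all three arms of the Biomarker Population, with the 95% CI of the mean percent change. Extend Table 5.0031 and its V600E copy, Table 5.0071, to Arms A and B and retitle them. Keep the Week 8 to Week 10 summary for Arms A and B.
2. In Protocol 9.2.1 and SAP 5.1, use one SD for both statements, or add a sentence saying what the 70% refers to. If it is the same quantity, add the 60% (±33.2%) and 70% (±38.8%) rows to Protocol Table 23 and SAP Table 1, and quote the precision at 70% beside the power.

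Cost: one or two sentences and two table rows in each document, and one extended display with its V600E copy, built from data already in Listing 25.0010. No extra patients, biopsies or tests are needed. The only drawback is a less favourable stated precision.
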